# Project proposal

**Title** A proof of principle study to evaluate the provision of a pictorial report following dental oral hygiene instruction to aid participants improving their gum health over a 4-week period

#### Introduction

According to the General Dental Council in the UK, it is the responsibility of the dental care team to provide patients with comprehensive and accurate preventative education and instruction in a manner which encourages their self-care and motivation (General Dental Council UK, 2012). Poor oral heath in patients is commonly reflected in dental plaque induced diseases, such as periodontal (gum) disease and dental caries (tooth decay). The accumulation of dental plaque and change in the dental microflora can lead to gingival inflammation, which in turn may progress to chronic periodontal disease and the eventual loss of affected teeth (Holt et al., 2000).

Plaque removal from teeth is a skill that can be accomplished only when a patient understands the goals of plaque removal and has been appropriately educated in practicing effective dental hygiene, including correct toothbrushing and the use of interdental cleaning tools. In recent years, cognitive behavioural techniques, such as the formation of goals, actions and written coping plans have been integrated with dental hygiene intervention (Philippot et al., 2005) and were found to be more effective than verbal oral hygiene instructions (Renz et al., 2007). Kreuter (2000) concluded that patient specific tailoring of treatment related to individual goals, may be more effective in reaching the health goals than the generalised "targeting approach" and suggested defining the term tailoring as: "any combination of information or change strategies intended to reach one specific person, based on characteristics that are unique to that person, related to the outcome of interest, and have been derived from an individual assessment". Thus, patient specific oral hygiene instructions (OHI) could be more effective than generic standardised OHI, particularly in the control of periodontal disease.

Oral health educators have important and valuable role within dental practices to promote good oral health care and work with patients to prevent disease such as gingivitis (reversible gum disease) and periodontitis (irreversible gum disease). Oral hygiene instructions (OHI) given by an oral health educator make a patient more aware of periodontal disease and consequently improve gingival health.

Non-invasive diagnostic aids have appeared in recent years. These devices rely on the principles of transillumination, laser and differential quantitative measurement of fluorescence or electrical impedance. However, their limited field of investigation and constraints on their use make them difficult to integrate into the daily dental practice. A new camera has been developed and is intended for clinical practice in general dentistry, directed towards preventive concepts, prophylactic care and overall patient management. The intraoral diagnostic camera (Soprocare Acteon® (PERIO mode and DAYLIGHT mode) improves visibility of all areas of tissue inflammation by utilising combination of blue light absorption by soft tissue and selective chromatic amplification.

The purpose of the study is to inform both the dental professional and patient about the condition of the oral tissues being examined. The camera can be used live because it does not emit ultraviolet or

ionising radiation, the PERIO mode informing practitioners about the presence of dental plaque while simultaneously enabling them to distinguish healthy from diseased gingival tissues.

This study will be Sponsored by the University of Bristol and funded by Acteon UK. The study will be undertaken by the Clinical Trials Unit within the University of Bristol Dental School.

#### Aims

The aim of this study is to estimate the effectiveness of the provision of patient specific oral hygiene instruction (OHI) with the use of a pictorial report following consultation with a dentist compared to standard verbally provided oral hygiene instruction with regards to patient plaque levels and improved gingival health, over a four-week period.

#### Primary Objectives

• To compare patient plaque levels and gingival health following the provision of enhanced OHI with a detailed pictorial report for the patient vs. the use of standard verbal OHI instructions alone over a 4-week period.

#### Secondary Objectives

- Patient perceptions of effectiveness of a having a pictorial report of their oral health as part of their dental care
- Patient attitudes to oral health measured at baseline and 4 weeks
- Participants' understanding of gingival health vs gingival disease
- Assessment of the accuracy of the intra-oral camera's ability to assess plaque levels compared to the clinician using traditional techniques using dye

#### Study Design

The study will be a parallel, randomised (1:1 ratio) 2 treatment, single centre study. The study sites will be the University of Bristol Dental School and Hospital including the South Bristol Community Hospital outreach centre, and the general dental practice Redland Park Dental Surgery. The study will be conducted by the Clinical Trials Unit team members who are part of Bristol Dental School.

At Visit 1, following provision of informed consent and confirmation of eligibility to take part in the study, participants will be provided with a questionnaire to complete regarding gum (gingival) health and then shown standard pictures of teeth and gingivae. They will be asked to indicate whether they think the pictures demonstrate oral health or oral disease and which they think represents their current oral health.

The participants will undergo an oral hard and soft tissue examination.

An intra-oral diagnostic camera will then be used by the clinician to take an intra-oral scan including images and a video of the patient's mouth. The images and video captured will be downloaded and a pictorial report prepared of their oral health. The camera software has the ability to detect plaque on the teeth and this will also be used to assess the levels of plaque present on the participant's teeth.

The study dentist will carry out a gum health examination (Modified Gingival Index, MGI) for the participant and will then measure the amount of plaque present using a traditional technique involving placing dye (food colouring) onto the surface of the teeth which highlights plaque (O'Leary et al 1972).

Participants will be randomised by study staff to one of 2 treatment groups (Control group - standard verbal oral health instructions (verbal OHI) or Test group – pictorial report + verbal oral health instructions (picture + verbal OHI) using a predetermined randomisation schedule.

The images captured will be downloaded and form a pictorial report of the health of the patient's mouth which will be provided to the patient. For those participants allocated to receive the pictorial report + verbal OHI (test group), the images and video captured will be explained to the patient so they can understand their current oral health. Participants assigned to receive standard verbal OHI alone will not be shown or have a review of the images collected by the intra-oral camera or be provided with a pictorial report of their current oral hygiene at Visit 1, however they will receive this at the end of the study.

For all participants, oral hygiene instruction will then be provided by a single dental clinician. This will be a different clinician from the clinician performing the dental assessments and scans of the mouth. For participants assigned to receive the pictorial report + verbal OHI (test group), they will be provided with oral hygiene instruction, a leaflet on oral health and a mouth mirror to use at home.

Participants will also receive questionnaires on their current oral hygiene practices and attitudes to oral health.

An appointment will be made for the patient to return to the study site in 4 weeks and they will be assessed for plaque levels and gingival health and a further scan of their mouth taken. For those participants assigned to receive the pictorial + verbal OHI, a pictorial report will be generated and reviewed alongside their initial report with the patient and advice provided for ongoing oral health maintenance.

For those participants who were assigned to receive standard verbal OHI alone, following the completion of study assessments at Visit 2, the dental clinician will then review the images of their mouth captured at both Visit 1 and Visit 2 and provide the patient with a copy of their pictorial report from both Visits to take away with them. These participants will also be provided with a mouth mirror and an information leaflet regarding the importance of maintaining good oral health along with advice for their individual ongoing oral health maintenance.

For each patient recruited to the study, they will be required to attend 2 study visits with the research team. The appointments are as outlined below:

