#### Visit 2: 4 weeks (approx.) following Visit 1: (approximately 30minutes)

- Confirm Eligibility
- Oral hard and soft tissue examination
- Completion of questionnaire with regards to current oral health/hygiene practices (Part A) and attitudes to oral health (Part B). (See Appendix 2)
- Final intra-oral scan download patient report
- Final plaque scores and gingival health assessments
- Provision of pictorial oral health report for patient to take away.
- For participants assigned to the standard verbal OHI alone, review of patient pictorial report obtained at Visit 1 and Visit 2 and provision of tailored OHI advice and a copy of their pictorial report, provision of mouth mirror and leaflet on oral health.

All assessments and the provision of oral hygiene instruction will be provided by a single dental clinician.

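### The protocol contradicts itself on whether the oral hygiene instructor is also the assessor, and does not expressly keep control participants' findings from the instructor at Visit 1

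*Protocol*

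**What the plan says.** The Aims section of the protocol sets the contrast: "provision of patient specific oral hygiene instruction (OHI) with the use of a pictorial report following consultation with a dentist compared to standard verbally provided" instruction. The test arm's advice is meant to be individual and the control arm's is not.

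At Visit 1 the individual findings are produced before anyone is instructed. Study Design has the camera scan first: "The images and video captured will be downloaded and a pictorial report prepared of their oral health". Scoring follows: "The study dentist will carry out a gum health examination (Modified Gingival Index, MGI) for the participant and will then measure the amount of plaque". Randomisation and instruction come after both, and the Visit 1 list keeps the scan and scores ahead of randomisation and instruction.

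On who instructs, Study Design says "For all participants, oral hygiene instruction will then be provided by a single dental clinician" and then "This will be a different clinician from the clinician performing the dental assessments and scans of the mouth". The Visit 2 section closes with a different statement: "All assessments and the provision of oral hygiene instruction will be provided by a single dental clinician".

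On what is withheld from the control arm, Study Design says: "Participants assigned to receive standard verbal OHI alone will not be shown or have a review of the images collected by the intra-oral camera". It also withholds the report until the end of the study. Study Design places the clinician's review of control images after the Visit 2 assessments, and the Visit 2 list places tailored advice for controls at that visit only. The Study Data section covers password-protected storage of scans and bars their use outside the protocol. It says nothing about which study clinicians may open them.

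**The concern.** The comparison depends on controls not receiving advice drawn from their own mouths during the four weeks. The Introduction cites a definition under which information is tailored if it rests on an assessment of that one person. On that definition, an instructor who tells a control where the plaque or inflammation lies is tailoring, even if no picture is shown. The rule for controls governs what the participant sees. It does not govern what the instructor knows.

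If some individual advice reaches controls by this route, the two arms become more alike. The estimated differences in plaque and gingival health would then understate the effect, and the report could not say exactly what the comparator was. The Sample Size section gives estimation as the purpose of this pilot, so a shrunken estimate matters even though no hypothesis test is planned.

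**Working it through.** The main check is a reading of the text, in four steps.

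**1. Do individual findings exist before control instruction?** Yes. In Study Design and in the Visit 1 list, the scan, the gingival score and the dye plaque score all precede randomisation and instruction, for every participant.

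**2. Who holds them when instruction is given?**

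| Passage followed | Instructor and assessor | What the instructor knows about a control at Visit 1 |
|---|---|---|
| Study Design | Two people | Nothing first-hand; access to report and scores not addressed |
| Visit 2 sentence, read as covering both visits | One person | Plaque and gingival findings, first-hand |
| Visit 2 sentence, read as covering Visit 2 only | Separate at Visit 1 | As in the first row |

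The Visit 2 sentence refers to all assessments without limiting itself to that visit, and it closes the schedule of both visits. The Study dental assessments section has one clinician do the baseline and 4-week scoring. On the wider reading, that person is also the instructor, which contradicts Study Design.

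**3. Does any passage stop the instructor from using the findings for a control?** Aims, Study Design, both visit lists, Study dental assessments, Items provided to patient, and Study Data were read for such a rule. The restrictions found are that controls are not shown the images, that they receive their report and other items only after the Visit 2 assessments, and that image review and tailored advice for them are scheduled then. These show the intent. None expressly withholds the report or scores from the instructor at Visit 1.

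**4. Direction and size.** Let D be the true difference in change between the arms, and c the share of that effect reaching controls through individual advice. Controls then improve by an extra c × D, so

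observed difference = D − c × D = D × (1 − c).

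With c = 0 there is no bias. Assumed values of 10%, 20% and 50% would leave 0.9 D, 0.8 D and 0.5 D. These only show the form of the bias: the protocol gives no basis for any value of c, and none is put forward.

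**The case against.** Several points weigh against this, and most of them limit it.

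- *One instructor for both arms is sound.* This stands in full. It removes differences between providers and is not criticised here.
- *The intent is clear.* Study Design separates the roles, the Visit 1 list makes the instruction depend on allocation, and tailored advice for controls waits until Visit 2. A leak would need the instructor to depart from the allocated arm. This stands as to intent, so it would be wrong to say that nothing protects the control arm. It does not remove the contradiction or supply a rule on access.
- *The Visit 2 sentence may concern Visit 2 only.* That is possible. The first-hand route then falls away, because control tailoring at Visit 2 follows the outcome assessments. The question of access to report and scores remains.
- *File handling may sit in a site manual.* It may. A conflict over who instructs still belongs in the protocol to settle.

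Three stronger readings are tempting and are not supported. A reader might infer that control advice could turn into the tested intervention. At Visit 1, however, controls get no images, explanation, report, leaflet or mirror, so at most part of the package could leak. A reader might ask for a fixed script for standard instruction. The protocol nowhere says that standard instruction is scripted or given without clinical information, so a script would redefine the comparator. A reader might also set a diluted effect against the precision of about 0.16 units in the Sample Size section. That figure is not a detection threshold. The section's own example interval, 0.607 to 0.772, has full width 0.772 − 0.607 = 0.165 and half-width 0.165 / 2 = 0.0825, so 0.16 is close to the full width. No such comparison is made here.

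**Conclusion.** The point holds in a limited form. The protocol gives two accounts of whether the instructor is the assessor. On one, the instructor has scored the control's teeth before giving standard advice. On the other, access to the control's report and scores is left open. This makes some contamination of the control arm possible but does not show that it will happen.

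The likely bias is towards zero. That rests on two assumptions: that patient-specific advice improves plaque and gingival health, and that the instructor would sometimes use what he or she knows. The size cannot be derived from the document. The change is worth making because it is nearly free and protects the contrast stated in the Aims. It is not a reason to doubt the design as a whole. Whether an assessor who also instructs would know the allocation is a separate question and is not argued here.

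**What to change.** Two changes to the protocol:

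1. Reconcile the closing sentence of the Visit 2 section with Study Design, so that the clinician who instructs is not the one who scans and scores.
2. Add to Study Design: *For participants in the verbal-only arm, the instructing clinician is not given the images, the pictorial report, or the plaque and gingival scores until that participant's Visit 2 assessments have been completed.*

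The cost is wording and minor file handling, since Study Design already provides for a separate instructor. The downside is that the instructor has less individual information about controls during the four weeks. The single instructor for both arms can stay.

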#### Visit 1: (Approximately 40 minutes)

- Consent
- Oral hard and soft tissue examination
- Eligibility

- Patient assessment of standard mouth images with dentist to look at the appearance of healthy vs non- healthy mouths (See Appendix 3)
- Intra-oral scan of patient's mouth and assessment of plaque download report for patient to take away (Appendix 5)
- Plaque and gingival health assessments (See Appendix 4)
- Randomisation
- Completion of questionnaire with regards to current oral health/hygiene practices (Part A) and patients' attitudes to oral health (Part B) (See Appendix 1 Parts a and b)
- Provision of OHI instruction by dentist depending on randomisation either standard verbal OHI **or** enhanced OHI (pictorial + verbal OHI) with a detailed pictorial report for the patient
- Provision of OH leaflet and mouth mirror for participants use at home for those participants assigned to the pictorial + verbal OHI group only.

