#### Secondary Objectives

- Patient perceptions of effectiveness of a having a pictorial report of their oral health as part of their dental care at Visit 1 and Visit 2
- Patient attitudes to oral health measured at Visit 1 and Visit 2
- Participants understanding of oral health vs oral disease at Visit 1 and Visit 2
- Assessment of the accuracy of the intra-oral camera's ability to assess plaque levels compared to the clinician using traditional techniques using dye

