#### Patient Oral Health Attitudes Questionnaire- Visit 2 – Part B

On a scale of 1 to 10, with 1 as 'Not at all' and 10 as 'extremely so' please rank the following statements accordingly:

- 7. Do you think bleeding gums and gum disease is a serious health concern 1 2 3 4 5 6 7 8 9 10 Not at all Extremely SO 8. If my bleeding gums are left untreated the likelihood that I will develop gum disease in the future is high 1 2 3 4 5 6 7 8 9 10 Not at all Extremely
- 9. Following my Oral Health plan over the last 4 weeks has improved the health of my mouth and reduce my risk of developing gum disease

1	2	3	4	5	6	7	8	9	10
Not at all									Extremely so

10. I know I can continue to follow my Oral Health plan in the future

1	2	3	4	5	6	7	8	9	10
Not at all									Extremely
									SO

11. Following my Oral Health plan will be difficult to maintain.

1	2	3	4	5	6	7	8	9	10
Not at all									Extremely so
12. My gun	n disease	concern	s me						
1	2	3	4	5	6	7	8	9	10
Not at all									Extremely so

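### The protocol fixes no single time for the Visit 1 practice and attitude questionnaires, so a pre-allocation baseline for these secondary outcomes is not secured

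*Protocol*

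**What the plan says.** Two statements make Visit 1 the reference point for attitudes. The Secondary Objectives that follow the aims list "Patient attitudes to oral health measured at baseline and 4 weeks", and the Secondary Objectives under Outcomes list "Patient attitudes to oral health measured at Visit 1 and Visit 2". Statistical Analyses treats secondary outcomes along the lines of the primary outcome, for which the reported quantity is a mean difference of change from baseline.

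Three places in the protocol bear on when the Visit 1 forms are completed:

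- **Study Design, opening account of Visit 1.** After consent and eligibility, "participants will be provided with a questionnaire to complete regarding gum (gingival) health and then shown standard pictures of teeth and gingivae". The examination, scan, MGI, plaque scoring and randomisation follow. This form is not identified as Part A or Part B.
- **Study Design, after randomisation.** Test participants have their images explained, and "For all participants, oral hygiene instruction will then be provided by a single dental clinician". After the leaflet and mirror, the text adds "Participants will also receive questionnaires on their current oral hygiene practices and attitudes to oral health".
- **Visit 1 list.** The entry beginning "Completion of questionnaire with regards to current oral health/hygiene practices (Part A" also names Part B. It stands directly after randomisation and directly before OHI.

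Appendix 1, Part B has six attitude items scored 1 to 10. Items 3, 4 and 5 concern the participant's oral health plan, and items 3 and 4 refer to the coming 4 weeks. Appendix 2 repeats the six items as 7 to 12; item 10 reads "I know I can continue to follow my Oral Health plan in the future".

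**The concern.** A baseline for a randomised comparison should be recorded before anything that differs between the arms can act on it. Here the comparison is open to participants by its nature: one arm is shown and taken through images of its own mouth at Visit 1, and the other is not. If Parts A and B are completed after allocation is known, or after the images have been explained, part of any arm difference in attitudes may already sit in the score called baseline. Change from that score then no longer estimates the whole effect. An analysis plan written later cannot recover a pre-allocation answer that was never collected.

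A second difficulty lies in the form itself. Three of its six attitude items presuppose a plan, so the form as printed does not suit any single moment of Visit 1.

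**Working it through.** The protocol states no figure on this point, so the check sets the passages side by side and then works out what the ordering does to the contrast.

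**Step 1: order of Visit 1 procedures**

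| Place in protocol | Order given | Are Parts A and B identified? |
|---|---|---|
| Study Design, opening account | gum-health questionnaire → pictures → examination → scan → MGI and plaque → randomisation | No |
| Study Design, after randomisation | images explained (test arm) → OHI, leaflet, mirror → questionnaires (text order only) | By subject, not by name |
| Visit 1 list | scan → plaque and gingival assessments → randomisation → Parts A and B → OHI and report | Yes |

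Apart from the image sheet in Appendix 3, the appendices show no other Visit 1 questionnaire. The gum-health form may therefore be Part A or Part B under another description, but the text does not say so. No place clearly puts Parts A and B before randomisation.

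**Step 2: effect on the change contrast**

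Let d1 be the true between-arm effect at 4 weeks. Let d0 be the shift of the test arm relative to control already present when the Visit 1 form is completed. Randomisation makes the expected arm difference zero before allocation, so

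expected difference in change = (arm difference at Visit 2) − (arm difference at Visit 1) = d1 − d0.

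- d0 = 0: the estimate is d1, with no bias.
- d0 = d1/2: the estimate is d1 − d1/2 = d1/2.
- d0 = d1: the estimate is d1 − d1 = 0.

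If d0 has the opposite sign to d1, the effect is overstated. If the Visit 1 score is used as a covariate instead, the loss depends on the slope of the Visit 2 score on the Visit 1 score. Both arms receive verbal OHI, so a shift common to both cancels; only a differential shift counts. The documents give no value for d0.

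**Step 3: Part B items at the two visits**

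| Visit 1 item | Visit 2 item | What changes |
|---|---|---|
| 3 | 9 | expected improvement becomes improvement experienced |
| 4 | 10 | able to follow the plan for 4 weeks becomes able to continue it in the future; both look ahead |
| 5 | 11 | difficult to do becomes difficult to maintain; both look ahead |

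The body of the protocol does not define the oral health plan. I take it to be the advice given at OHI. On that assumption, items 3 to 5 asked before OHI refer to something the participant has not received. Asked after OHI they make sense, but if the whole form is moved there, items 1, 2 and 6 are answered after test participants have seen their images.

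**Step 4: scope**

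Plaque and MGI come before randomisation both in Study Design and in the Visit 1 list. So does the Appendix 3 picture task.

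**The case against.** The strongest reply is that the Visit 1 list governs. Study Design closes by referring the reader to the visit outlines, and the Visit 1 list is the only ordered account that names Parts A and B. There they come before OHI and before the report. The Study Design sentence on questionnaires merely adds an item and carries no time word, whereas the OHI sentence does mark sequence. A reader might infer from the text order that the baseline is contaminated by the intervention. The documents do not support that as a fact: on the list's order the most that can have acted is knowledge of allocation, and the protocol does not say when participants learn it. This part of the reply stands.

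A reader might also infer that items 3 to 5 all turn from expectation into experience at Visit 2. Only item 3 does.

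It is also fair to say that much of Part A records settled habits and facts, such as brushing frequency, handedness and toothpaste, which a report seen minutes earlier would hardly change. Self-rated oral health, concern and motivation are more exposed. And this is a 20-participant pilot sized for estimation, with the questionnaires secondary.

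What the reply does not remove is that even the list puts the forms after randomisation, and that on the list's order items 3 to 5 ask about a plan not yet given.

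**Conclusion.** The point holds as an unresolved inconsistency that leaves a baseline exposed. The three accounts do not agree, and none clearly secures the pre-allocation attitude score on which the secondary objective relies. The possible bias in a change contrast is d0: nothing if the forms are in practice completed before participants know their allocation, and up to the whole effect if the immediate shift equals the 4-week one. Its size and sign cannot be taken from the documents. This rests on the secondary analyses following the primary one in using change from baseline, as Statistical Analyses indicates.

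Separately, and whatever the timing, a change score on items 3 to 5 compares differently worded questions, most clearly for item 3.

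Only the secondary practice and attitude questionnaires are affected. The plaque and MGI baselines are not. The change is worth making because it is nearly free and analysis cannot repair the omission afterwards.

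**What to change.** Give one order for Visit 1 and use it in both accounts within Study Design and in the Visit 1 list:

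1. Part A and Part B items 1, 2 and 6 are completed after consent and before the scan and randomisation. Say whether the gum-health questionnaire in Study Design is one of these forms.
2. Part B items 3 to 5 are completed after OHI and labelled as post-instruction expectations. Compare them between arms at each visit, and do not analyse them as change from baseline.

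The Visit 2 list already puts the questionnaires ahead of the scan, so the first step also brings the two visits into line.

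The cost is a reordering of Visit 1 and one questionnaire page split in two, which means handing out forms twice. No assessment is added.
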